1. LIST OF ABBREVIATIONS

AE(s) Adverse Event(s)

ADE Adverse Device Effect

eCRF(s) Electronic Case Report Form(s)

DMP Data Management Plan

e.g. *exempli gratia* (for example)

ESH European Society of Hysteroscopy

EQ-5D EuroQuol 5 dimension (patient questionnaire)

FAS Full Analysis Set

FDA Food and Drug Administration

FIGO International Federation of Gynecology and Obstetrics

HMB Heavy Menstrual Bleeding
IUUS Intrauterine Ultrasound

ICH International Conference on Harmonization

N Number (sample size)
OTE Overall Treatment Effect

SADE Serious Adverse Device Effect

SAE(s) Serious Adverse Event(s)

SAS® Statistical Analysis System (SAS® Institute Inc., Cary, NC)

SD Standard Deviation

UADE Unanticipated Adverse Device Effect

2. INTRODUCTION

The Sonata System combines intrauterine ultrasound (IUUS) with radiofrequency (RF) ablation in a single handpiece, enabling transcervical visualization and ablation of uterine fibroids without incisions. Sonata is intended to provide focal treatment of symptomatic fibroids responsible for heavy menstrual bleeding (HMB). This Statistical Analysis Plan (SAP) describes the analytical methods to be used to assess the safety and effectiveness of the Sonata System in the treatment of symptomatic uterine fibroids.

3. STUDY OBJECTIVES

The objective of this study is to document the presence or absence of newly formed intrauterine adhesions after treatment with the Sonata System when used in women with submucous and/or transmural fibroids in accordance with product labeling.

4. INVESTIGATIONAL PLAN

4.1 Overall Study Design

The study is designed as a post-market prospective, multicenter, single-arm cohort study.

4.1.1 Schedule of Screening and Study Assessments

Table 1: Schedule of Screening and Study Assessments

Aggaggment	Congont	Baseline and	Follow up	
Assessment	Consent		Treatment	6 wks
Informed Consent	X			
Demographics		X		
Transvaginal sonography		X^1		
Hysteroscopic assessment of uterine cavity		X^1		X
Sonata Treatment & Procedure Assessments			X^1	
Adverse events			X	X
EQ-5D		X		X
OTE and Subject Satisfaction				X
Return to normal daily activity/Treatment Recovery Questionnaire				X
Pregnancy and pregnancy outcome / surgical reintervention*				X

^{*} If subject undergoes hysterectomy, operative and pathology reports shall be forwarded to study sponsor

¹ As per routine medical care

4.2 Selection of Study Population

4.2.1 Inclusion Criteria

- 1) Have selected Sonata for treatment of fibroids in the presence of heavy menstrual bleeding
- 2) Presence of at least one submucous myoma (type 1, type 2) or transmural fibroid (type 2-5)
- 3) Are \geq 18 years of age at the time of enrollment
- 4) Willing and able to read, understand, and sign the informed consent form and to adhere to all study follow-up requirements

4.2.2 Exclusion Criteria

- 1) Preexisting adhesions within the endometrial cavity as indicated by an ESH score \geq I as determined by the investigator
- 2) One or more Type 0 fibroids and/or endometrial polyps of any size
- 3) Any reason for which, in the opinion of the Investigator, the individual study patient is not appropriate or suitable for participation in this study

4.3 Treatments

The Sonata System is a CE-marked device and is used within its intended purpose in this study. The treatment shall be performed in accordance with the Sonata System Operator's Manual. Sponsor representatives may assist the Investigator (generally one to three individuals) and may be present during the procedure to provide equipment support if needed as well as for proctoring and general observation.

4.4 Data Management

Data collected for the study will be entered into a web-based system through electronic Case Report Forms (eCRFs) by each study site. The Electronic Data Capture (EDC) system maintains a complete electronic audit trail. The design and specification of eCRFs as well as edit checks will be in accordance with the study requirements. For statistical analysis, data stored in the central database will be exported to SAS® files (SAS Institute Inc, Cary, NC, USA). The data extract from the final locked database will be used to generate the final clinical study report.

Prior to database lock, the following steps must be completed: data entry or transferring as required per protocol, source verification, query resolution, data review by clinical data managers and final sign-off by site principal investigators.

4.5 Efficacy and Safety Variables

4.5.1 Primary Efficacy Variables

4.5.1.1 Incidence of Newly Formed Intrauterine Synechiae at Six Weeks

Incidence of newly formed intrauterine synechiae at six weeks will be assessed via diagnostic hysteroscopy, with any adhesions classified per the European Society of Hysteroscopy (ESH) scoring system (see Appendix D). Diagnostic hysteroscopy will be captured on digital video and forwarded to two independent readers. In the event of a disagreement in ESH score between the readers, a third independent reader will perform a tiebreaker review.

4.5.1.2 Surgical Reintervention

Subjects will be asked to indicate whether any of their adverse events required a surgery or procedure. The rate of surgical reintervention due to treatment failure will be evaluated throughout all assessment timepoints. Surgical reintervention for the treatment of HMB includes the following procedures:

- a) Hysterectomy (abdominal, vaginal, laparoscopic)
- b) Myomectomy (abdominal, vaginal, laparoscopic, hysteroscopic)
- c) Uterine artery embolization
- d) Magnetic resonance-guided focused ultrasound (MRgFUS) or similar focused ultrasound treatment
- e) Endometrial ablation (nonresectoscopic, hysteroscopic)

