4.5.4.1.1 Adverse Event Definitions

- A. Adverse Event (AE) Any untoward medical occurrence, unintended disease or injury or any untoward clinical signs (including a clinically significant abnormal laboratory finding) in subjects, users or other persons whether or not related to the Sonata System.
 - 1) This includes events related to the procedures involved.
 - 2) For users or other persons this is restricted to events related to the Sonata System or it's procedure
 - 3) Increase in frequency or severity of symptoms relative to baseline are considered an adverse event if they are not related to a measured endpoint
- NOTE 1: An elective surgical reintervention for HMB is not considered an adverse event.
- NOTE 2: Presence of adhesions discovered during follow-up are not considered as an adverse event
- NOTE 3: Inpatient admission does not constitute hospitalization for the purposes of this protocol as long as there are no reported adverse events associated with the stay

B. **Serious Adverse Event (SAE)** – Adverse Event that led to

- 1) Death
- 2) A serious deterioration in the health of the subject that either resulted in:
 - A life-threatening illness or injury, or
 - A permanent impairment of a body structure or a body function, or
 - An in-patient hospitalization, or prolongation of existing hospitalization, of more than 24 hours, or
 - A medical or surgical intervention to prevent life threatening illness or injury or permanent impairment to a body structure or a body function.
- 3) Fetal distress, fetal death or congenital abnormality or birth defect

NOTE 1: A planned hospitalization for a pre-existing condition, or a procedure required by the clinical investigational plan, without a serious deterioration in health, is not considered to be a serious adverse event.

NOTE 2: If recovery time from treatment with the Sonata System is no longer than expected and site scheduling prevents same-day discharge, overnight stay is not considered prolonged

- C. **Adverse Device Effect (ADE)** Adverse Event related to the use of a medical device. This includes:
 - 1) Any adverse event resulting from insufficiencies or inadequacies in the instructions for use, the deployment, the installation, the operation, or any malfunction of the Sonata System.
 - 2) This definition includes any event that is a result of a use error or intentional misuse.

D. Device Deficiency

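### Section 4.5.1.2 asks about reintervention only through adverse events, although an elective reintervention for HMB is not an adverse event; the SAP should name the Table 1 item as the source of the rate

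*SAP*

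**What the plan says.** Surgical reintervention is section 4.5.1.2 of the SAP and falls under the heading "4.5.1 Primary Efficacy Variables". That section has three parts:

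- the question put to the subject: "Subjects will be asked to indicate whether any of their adverse events required a surgery or procedure";
- the quantity to be reported: "The rate of surgical reintervention due to treatment failure will be evaluated throughout all assessment timepoints";
- the events that count: "Surgical reintervention for the treatment of HMB includes the following procedures", followed by items a) to e) (hysterectomy, myomectomy, uterine artery embolization, focused ultrasound, endometrial ablation).

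Section 4.5.4.1.1 defines adverse events. NOTE 1 under item A reads "An elective surgical reintervention for HMB is not considered an adverse event". Item A.3 deals with symptoms: "Increase in frequency or severity of symptoms relative to baseline are considered an adverse event if they are not related to a measured endpoint".

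Table 1 in section 4.1.1 has a row, apart from the adverse events row, for "Pregnancy and pregnancy outcome / surgical reintervention", marked at six weeks only. Its footnote has operative and pathology reports sent to the sponsor after a hysterectomy, with no condition that an adverse event was reported.

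Section 4.6.4.1, the primary efficacy analysis, covers adhesions only. Nothing under 4.6.4 gives a data source, numerator or denominator for reintervention.

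**The concern.** The question and the variable are built on different events. The question reaches a procedure only through an adverse event that required it. The variable is meant to count procedures undertaken because treatment did not control the bleeding, and a woman may choose such a procedure without any adverse event, as the SAP defines one, having occurred.

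If the answers to that question supplied the numerator, elective procedures for HMB with no underlying adverse event would go uncounted. Omissions of this kind can only lower the reported failure rate, which favours the device. In a descriptive study of at most 60 women, one or two omissions could decide whether the report shows any reintervention at all.

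**Working it through.** The SAP states no expected reintervention rate and no derived sample size, so there is no figure to reproduce. The check is mainly one of consistency, followed by an illustration of size.

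**Consistency**

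1. Take a woman whose HMB persists after treatment and who elects a hysteroscopic myomectomy before the six-week visit. The procedure is in item b) of 4.5.1.2 and is done for HMB, so she belongs in the numerator.
2. Is the procedure an adverse event? No, by NOTE 1.
3. Is the bleeding behind it an adverse event? Under A.3 a symptom qualifies only if it has increased since baseline and is not related to a measured endpoint. Persistent HMB is not an increase. Worsened HMB is arguably related to measured endpoints: reintervention for HMB itself, and the Overall Treatment Effect, which rates change in fibroid symptoms (4.5.2.1). The SAP does not define a measured endpoint, so this last step is likely rather than certain.
4. With no adverse event, her truthful answer to the 4.5.1.2 question is no. She meets the endpoint and the question does not find her.
5. The Table 1 row could find her. The SAP does not say what that row asks or that the rate is derived from it. The footnote on reports concerns hysterectomy, item a), and not items b) to e).

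**Size per missed case**

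Input: up to 60 subjects (4.6.8). Each missed case lowers the rate by 1/60 = 1.7 percentage points. As 60 is the maximum, this is the smallest loss per case; a smaller denominator makes it larger. Missing the only case turns 1/60 = 1.7% (exact 95% interval 0.0 to 8.9%) into 0/60 = 0% (0 to 6.0%). For comparison, 3/60 = 5.0% has the interval 1.0 to 13.9%.

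**Illustration if the adverse-event question were the only source**

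Assumptions, none of them from the SAP: true rate π of 2, 5 or 10%; share e of reinterventions with no adverse event behind them of 0, 50, 90 or 100%; n = 60.

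Expected counted rate = π(1 − e). Chance of counting none = [1 − π(1 − e)]^60.

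| π | e = 0 | e = 50% | e = 90% | e = 100% |
|---|---|---|---|---|
| 2% | 2.0%; 0.30 | 1.0%; 0.55 | 0.2%; 0.89 | 0%; 1.0 |
| 5% | 5.0%; 0.046 | 2.5%; 0.22 | 0.5%; 0.74 | 0%; 1.0 |
| 10% | 10.0%; 0.002 | 5.0%; 0.046 | 1.0%; 0.55 | 0%; 1.0 |

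Each cell gives the expected counted rate, then the chance of counting none. For example, with π = 5% and e = 50%: 0.05 × 0.5 = 2.5%, and 0.975^60 = 0.22, against 0.95^60 = 0.046 with full capture.

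If the Table 1 item is the source and is asked without reference to adverse events, the e = 0 column applies throughout.

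**The case against.** The strongest reply is that capture outside the adverse event system is already scheduled. Table 1 separates reintervention from adverse events, and NOTE 1 fits that separation: it keeps an efficacy outcome out of the safety listing and is no error in itself. Section 4.5.1.2 never says that the rate is calculated from the adverse-event question. How the Table 1 row is worded may be settled in the protocol or the eCRFs, which are not at hand. The stated objective concerns adhesions only, and the study is exploratory.

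Much of this stands. A reader might infer that the trial misses every elective reintervention, or that the reported rate is biased towards zero in the device's favour. The SAP does not support either inference, because nothing says that the Table 1 row is disregarded. Nor would the question miss every target event: NOTE 1 concerns elective procedures, and a listed procedure required by a reported adverse event would still be found. A yes prompted by surgery for an unrelated adverse event need not inflate the rate either, since 4.5.1.2 limits the variable to listed procedures for HMB, provided the indication is recorded.

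The reply does not remove the conflict. Sections 4.5.2.1 and 4.5.2.2 open by saying what subjects will be asked, and that is how those variables are collected. Section 4.5.1.2 opens in the same way, so the natural reading is that its question collects its variable. It is the only wording the SAP gives for asking about reintervention, and no analysis section points to Table 1 instead. The exploratory label does not help, because a descriptive rate depends entirely on correct counting.

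**Conclusion.** The point holds as a conflict between a stated question and the variable it introduces. Followed as written, the question in 4.5.1.2 would not reach elective procedures for HMB that have no adverse event behind them. Loss of such cases is a risk, not an established fact: it occurs if the adverse-event question supplies the numerator, and need not occur if the Table 1 item does. The SAP does not choose between them.

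In the first case the bias is downward, at 1.7 percentage points per missed case with 60 women. The total cannot be estimated from the document, since neither the reintervention rate nor the share without an adverse event is given. The conclusion assumes that persistent HMB falls outside A.3, which its wording makes likely. Confidence is moderate. The correction should be made because the variable is listed as primary and the change is small.

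**What to change.** Replace the first sentence of 4.5.1.2 with wording such as:

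> At Week 6 each subject is asked whether she has undergone any procedure listed in a) to e) since treatment, whether or not an adverse event was reported. The date and indication (HMB/treatment failure, or other) are recorded. The rate is derived from the surgical reintervention item in Table 1 and counts procedures performed for HMB/treatment failure.

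Move the question about surgery required for an adverse event to the safety section and tabulate it there separately.

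The cost is a change of SAP wording and the use of an item that Table 1 already schedules. No visit or procedure is added. If the eCRF for that item does not yet hold the date and indication, those fields need to be added or queried before database lock.

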4.5.2 Secondary Efficacy Variables

4.5.2.1 Overall Treatment Effect (OTE)

Subjects will be asked to indicate whether their uterine fibroid symptoms have improved, remained the same, or worsened. If the subject indicates that her symptoms have improved, she will be asked to rate the degree of improvement on a 7-point scale from "almost the same, hardly better at all" (1) to "a very great deal better" (7). If the subject indicates that her symptoms worsened, she will be asked to rate the degree of worsening on a 7- point scale from "almost the same, hardly worse at all" (-1) to "A very great deal worse" (-7). A copy of the questionnaire is included as Appendix C.

4.5.2.2 Subject Satisfaction

Subjects will be asked to rate their satisfaction with the treatment, with responses based on a 6-point Likert scale ranging from "very satisfied" to "very dissatisfied". They will also be asked if they would recommend the treatment to a friend with the same health problems using a 4-point scale from "definitely yes" to "definitely not".

4.5.3 Procedure Variables

Procedure information will be captured within the eCRF. The device insertion and removal times will be collected to facilitate the calculation of procedure time. Additionally, the time and date of discharge will be collected. The anesthesia and procedure-related medications, and number and size of each fibroid treated will also be captured, along with the number of ablations for each fibroid.

4.5.4 Safety Variables

4.5.4.1 Adverse Events

Adverse events will be reported and classified by the Investigator using the specific medical diagnosis, or using signs, symptoms or abnormal laboratory values if no medical diagnosis can be identified.

4.5.4.1.1 Adverse Event Definitions

- A. Adverse Event (AE) Any untoward medical occurrence, unintended disease or injury or any untoward clinical signs (including a clinically significant abnormal laboratory finding) in subjects, users or other persons whether or not related to the Sonata System.
 - 1) This includes events related to the procedures involved.
 - 2) For users or other persons this is restricted to events related to the Sonata System or it's procedure
 - 3) Increase in frequency or severity of symptoms relative to baseline are considered an adverse event if they are not related to a measured endpoint
- NOTE 1: An elective surgical reintervention for HMB is not considered an adverse event.
- NOTE 2: Presence of adhesions discovered during follow-up are not considered as an adverse event
- NOTE 3: Inpatient admission does not constitute hospitalization for the purposes of this protocol as long as there are no reported adverse events associated with the stay

B. **Serious Adverse Event (SAE)** – Adverse Event that led to

- 1) Death
- 2) A serious deterioration in the health of the subject that either resulted in:
 - A life-threatening illness or injury, or
 - A permanent impairment of a body structure or a body function, or
 - An in-patient hospitalization, or prolongation of existing hospitalization, of more than 24 hours, or
 - A medical or surgical intervention to prevent life threatening illness or injury or permanent impairment to a body structure or a body function.
- 3) Fetal distress, fetal death or congenital abnormality or birth defect

NOTE 1: A planned hospitalization for a pre-existing condition, or a procedure required by the clinical investigational plan, without a serious deterioration in health, is not considered to be a serious adverse event.

NOTE 2: If recovery time from treatment with the Sonata System is no longer than expected and site scheduling prevents same-day discharge, overnight stay is not considered prolonged

- C. **Adverse Device Effect (ADE)** Adverse Event related to the use of a medical device. This includes:
 - 1) Any adverse event resulting from insufficiencies or inadequacies in the instructions for use, the deployment, the installation, the operation, or any malfunction of the Sonata System.
 - 2) This definition includes any event that is a result of a use error or intentional misuse.

D. Device Deficiency

As this is a clinical trial utilizing a CE-marked device, device efficiencies ("incidents") are collected and reported by Gynesonics, Inc. according to Gynesonics' Complaint Handling system and per MEDDEV 2.12.1.

If the device deficiency involves an adverse event category as described in this protocol, the investigator shall notify the Sponsor by completing the adverse event or death case report form as applicable and must provide the Sponsor with all necessary documentation needed. If the device deficiency does not involve a reportable adverse event per this protocol, the investigator should notify the Gynesonics, Inc. Complaint Coordinator by emailing the information about the device deficiency to: [contact].

- E. **Serious Adverse Device Effect (SADE)** Adverse device effect that has resulted in any of the consequences characteristic of a serious adverse event.
- F. Unanticipated Serious Adverse Device Effect (USADE) Serious adverse device effect which by its nature, incidence, severity or outcome has not been identified in the current version of the risk analysis report.

As this clinical trial is conducted according to the Sonata System's approved CE mark labeling, within its approved indications, and in accordance with its instructions for use, the Investigator and sponsor will follow the Medical Device Vigilance Guidelines (per MEDDEV 2.12.1) and report adverse events according to that guideline.

G. **Anticipated** - An effect which by its nature, incidence, severity or outcome has been previously identified in the risk analysis

4.5.4.1.2 Adverse Event Evaluations

Each adverse event in the study will be evaluated by the investigator as to its severity, its relationship to the study device and to the procedure, and whether it was anticipated in the investigational plan. The distinction between an AE, an SAE, and a UADE will be made according to the definitions given above. Gynesonics is responsible for the classification of adverse events. In case of disagreements in which the investigator's evaluation is that the event is more serious and/or more related, both opinions will be included in adverse event reports.

4.5.4.1.3 Relatedness

The determination of the level of relatedness of the adverse event to the Sonata device or Sonata procedure will be made according to the definitions below. Adverse events considered to be "Related", "Possibly Related", or "Not Related" to the Sonata System will be classified as an ADE or an SADE for purposes of statistical analysis.

- 1) Related: The adverse event was directly and clearly related to the Sonata System or procedure.
- 2) Possibly Related: The adverse event may have been related to Sonata System or procedure, but an alternative cause is equally likely.
- 3) Not Related: The adverse event was not related to the Sonata System or procedure.

Complications of procedures in the study are considered not related if the said procedures would have been applied to the subject also in the absence of the study device use/application.

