4.6.7 Safety Analyses

4.6.7.1 Adverse Events

Procedure safety will be assessed by recording all AEs that occur on the day of the treatment procedure. Longer-term safety will be assessed by recording at the follow-up visit any untoward medical occurrence since baseline. Each AE will be assessed for relationship to study device and/or procedure. In addition to evaluating procedural and longer-term safety, subjects who become pregnant after the procedure will be asked to report any pregnancy complications.

Descriptions of AEs will include the date of onset, the date the AE resolved, stabilized, or returned to baseline, and the outcome. All reported AEs will be summarized by the number of subjects reporting AEs, seriousness, and relationship to the Sonata System device and/or procedure. Summaries will also be presented for device-related AEs, and procedure-related AEs.

AEs will be summarized both by subject incidence rate and event incidence rate. In addition, AEs will be summarized by relationship to the Sonata System procedure and/or device, such that each subject will be counted only once for each AE by using the AE with the greatest relationship within each category. The sponsor is responsible for classifications of adverse events. Both investigator reported and sponsor evaluated classifications will be summarized.

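### The ADE/SADE classification rule takes in events graded Not Related, so as written every AE is an ADE and every SAE is a SADE

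*SAP*

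**What the plan says.** SAP section 4.5.4.1.3 (Relatedness) grades each adverse event on a three-level scale: Related, Possibly Related and Not Related. Before defining the levels it gives the rule for using them: "Adverse events considered to be 'Related', 'Possibly Related', or 'Not Related' to the Sonata System will be classified as an ADE or an SADE". The sentence goes on to say that this classification is for the statistical analysis, so it is an analysis rule and not only a reporting convention. The third level is then defined as follows: "Not Related: The adverse event was not related to the Sonata System or procedure".

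The labels themselves are defined in 4.5.4.1.1:

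- An adverse event (AE) counts "in subjects, users or other persons whether or not related to the Sonata System". For subjects, relatedness plays no part.
- An ADE (item C) is an "Adverse Event related to the use of a medical device".
- A SADE (item E) is an "Adverse device effect that has resulted in any of the consequences characteristic of a serious adverse event".

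Section 4.5.4.1.2 has the investigator assess each event for "its relationship to the study device and to the procedure". On output, 4.6.7.1 plans AE summaries by seriousness and by relationship, and adds: "Summaries will also be presented for device-related AEs, and procedure-related AEs". It does not say which relatedness levels make an event device-related or procedure-related.

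**The concern.** A rule that assigns a device-effect label should separate events attributed to the device from those that are not. This one names every level on the scale and so separates nothing. It places events graded Not Related in categories that, by the SAP's own definitions, require a relation to the device.

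Any ADE or SADE count produced under the rule would be an all-cause AE or SAE count under a device-effect label. The same could happen to the device-related summary in 4.6.7.1. The SAP has no other statement that maps relatedness levels to device effects for analysis, so a programmer looking for a cut-off could reasonably take this one. The programmer must otherwise depart from the SAP without any text to support it.

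**Working it through.** The SAP states no figure on this point, so there is none to reproduce. The check is a comparison of the rule with the definitions, followed by simple arithmetic on its size.

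**Step 1: enumerate the cases.** The inputs are the three relatedness levels (4.5.4.1.3) and two seriousness states (serious or not, 4.5.4.1.1 item B), giving 3 × 2 = 6 cells. The last column applies items C and E and counts Possibly Related as related. The rule in 4.5.4.1.3 does count it, although items C and E do not mention that level.

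| Relatedness | Serious | Rule as written (4.5.4.1.3) | Definitions (items C and E) |
|---|---|---|---|
| Related | No | ADE | ADE |
| Related | Yes | SADE | SADE |
| Possibly Related | No | ADE | ADE |
| Possibly Related | Yes | SADE | SADE |
| Not Related | No | ADE | AE only |
| Not Related | Yes | SADE | SAE only |

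As written, 6 of 6 cells are device effects and all 3 serious cells are SADEs. Since a SADE is itself an ADE, the ADE set is all AEs and the SADE set is all SAEs. Under the definitions, 4 of 6 cells are ADEs and 2 of those 4 are SADEs. Rule and definitions disagree on both Not Related cells.

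**Step 2: look for a correcting passage.** None was found.

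- The end of 4.5.4.1.3 treats some procedure complications as not related. Under the rule this has no effect on ADE or SADE status, because not-related events are labelled device effects anyway.
- Section 4.5.4.1.2 refers back to the definitions for telling AE, SAE and UADE apart, but does not list ADE or SADE.

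**Step 3: size.** Let N be the number of AEs and q the share graded Not Related. The rule counts N ADE events, and the definitions count N(1 − q). The overstatement is N / [N(1 − q)] = 1/(1 − q). The SAP gives no q, so these values are assumed:

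| q (assumed) | 1/(1 − q) |
|---|---|
| 0.10 | 1/0.90 = 1.11 |
| 0.25 | 1/0.75 = 1.33 |
| 0.50 | 1/0.50 = 2.00 |
| 0.75 | 1/0.25 = 4.00 |

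The formula holds for SADE events with q taken among SAEs. These are ratios of events. The subject-level ratio is women with any AE divided by women with at least one Related or Possibly Related AE, and q alone does not determine it. The distinction matters because 4.6.7.1 reports both subject and event incidence.

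**The case against.** The strongest case on the other side is that no planned output clearly depends on the rule. Section 4.6.7.1 is the only AE analysis section and never uses the labels ADE or SADE. Its tables by relationship count each subject at the greatest relationship, so Not Related can stay a separate row. Nothing says that the device-related summary takes its cut-off from 4.5.4.1.3, and putting an event graded Not Related into such a summary would offend plain language. The study is exploratory and descriptive, and the sentence looks like a drafting slip.

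Most of this stands as a limit on impact. It does not remove the contradiction: the sentence expressly governs the analysis, names the third level outright and is corrected nowhere.

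Two narrower objections also have force:

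- Items C and E do not mention Possibly Related. Counting that level rests on the same sentence that contains the error. Nothing in the SAP contradicts keeping it, but Related plus Possibly Related is the likely intent and not a stated one.
- The factor 1/(1 − q) is an identity with every q assumed, so it says nothing about this trial's events. If only Related counted, the denominator would be smaller and the overstatement larger whenever any event is graded Possibly Related.

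**Conclusion.** The concern holds. The rule in 4.5.4.1.3 is wrong as written: it contradicts its own definition of the third level and items C and E of 4.5.4.1.1, and it makes the ADE and SADE labels uninformative. The unanticipated category in item F is built on SADE, so it could also draw in unrelated serious events, although the reference in 4.5.4.1.2 back to the definitions weighs against that reading.

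The contradiction itself needs no assumption. The size does: ADE events are overstated 1.11 to 4.00 times for assumed q from 0.10 to 0.75, with Possibly Related counted as related. The effect on the device-related summary is conditional on its cut-off being taken from this rule. The tables by relationship can be correct as planned, and the primary adhesion analysis in 4.6.4.1 is untouched. The sentence should be corrected before programming; the point does not threaten the study's main result.

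**What to change.** In 4.5.4.1.3, remove the third level from the rule and join the remaining two with *or*, so that only events graded Related or Possibly Related "will be classified as an ADE or an SADE for purposes of statistical analysis". The sponsor should confirm that these two levels are the intended cut-off, and the sentence should be reconciled with items C and E of 4.5.4.1.1.

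Two clarifications belong with the correction:

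- In 4.5.4.1.3, say whether an event related only to the procedure is an ADE. The level definitions pool system and procedure, item C refers to use of a device, and 4.5.4.1.2 and 4.6.7.1 treat device and procedure separately.
- In 4.6.7.1, state that the device-related and procedure-related summaries count the same levels, with Not Related excluded.

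The cost is a few words changed in one sentence and one added sentence in each of the two sections. No new data are needed.
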